9.6 Patient Characteristics and Significant Protocol Violations

Demographic and other baseline data will be summarized descriptively for all patients in the ITT set. Comparisons between the two groups will be performed using Pearson's chi-square tests and Student's t-tests. Significant protocol violations will be documented.

9.7 Disposition

The number of enrolled subjects will be summarized in a flow chart with frequency of completion and discontinuation. The subjects discontinued from BtB and their corresponding information will be listed. Significant protocol violations will be tabulated and/or listed.

9.8 Compliance

Compliance status will be tabulated for the BtB arm.

9.10 Analysis Plan for the Primary Objective

To test our primary hypothesis, an analysis of covariance (ANCOVA) will be performed to test for treatment group differences in Week 12 FMD adjusted for baseline FMD using the intent-to-treat set. Statistical significance will be considered if two-sided p-value <0.05. This analysis will be also repeated using the per-protocol set.

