Each individual participant will be followed for approximately 28 weeks (up to 4 weeks from screening to randomization and 24 weeks on study). We expect to enroll 3-4 participants per month. The total duration of this study will be approximately 38 months.

POPULATION

All participants will be HIV-infected, 18 years of age or older, have achieved HIV-1 viral loads less than 75 copies/mL while receiving stable ART for at least 12 months, and have a PHQ-9 score ≥ 10 . Participants will be recruited from the infectious diseases outpatient clinics of Eskenazi Health Hospital and the Indiana University Health Hospitals.

SAMPLE SIZE

The total sample size for this study will consist of 110 enrolled participants. Up to 200 participants may be screened to identify the 110 eligible for enrollment. If a consented and otherwise eligible participant withdraws prior to the Baseline/Entry Visit, this participant will be replaced.

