3.3 First Entry Visit

This visit will occur within 15 days of the Screening Visit and will occur at the ICRC. The primary purpose of this visit is to perform the first of two FMD studies and to obtain blood for the circulating markers of interest. Two Entry Visits are being conducted in order to establish more precise and stable estimates of endothelial function, inflammation, and coagulation prior to randomization. **The study participant must be fasting for this visit.** At this visit, FMD will be performed and blood will be obtained after vital signs are

measured and the PHQ-9 questionnaire administered. A urine pregnancy test will be repeated for women of reproductive potential. Blood and urine samples will be obtained for archiving.

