3.4 Second Entry Visit

This visit will occur within 30 days of the Screening Visit and will occur at the ICRC. During this visit, updated psychiatric management (such as new medical or behavioral therapies initiated since screening) and medications will be reviewed. The PHQ-9, SCL-20, International Physical Activity, Morisky, Tobacco Use, General Anxiety Disorder-7, Buss-Perry Aggression, PANAS (Positive Affect subscale of the Positive and Negative Affect Schedule), and Pittsburgh Sleep Quality Index questionnaires will be administered. **The study participant must be fasting for this visit.** Vital signs will be measured and a brief physical examination will be performed prior to performing the FMD procedure and obtaining blood for the circulating markers of interest. A urine pregnancy test will be repeated for women of reproductive potential. Urine will also be obtained for archiving.

Blood will also be drawn at this visit for archiving DNA for future studies of interest linking genetics with endothelial function and depression scores.

Randomization will occur at this visit. Randomization will be stratified by use of pharmacologic antidepressants at the time of the Second Entry Visit. The participants' primary providers will be notified of the randomization assignment.

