3.6 Brachial artery reactivity indices

FMD and NTGMD will be measured according to established guidelines (126) at both Entry Visits, the Week 12 Visit, and the Week 24 Visit. These measurements will be performed at the ICRC.

Brachial reactivity measurements have considerable day-to-day variability. Variables that will transiently affect vasomotor function include environmental conditions, tobacco and alcohol use, diet, and medications (127). Therefore, it is desirable to control these factors in order to obtain results that more accurately reflect the underlying condition being studied. Therefore, the room temperature will be controlled at 68-71°F. The participant will rest supine for 10 minutes prior to imaging. Participants will be told to not use tobacco-containing products or eat or drink anything other than water for 8 hours prior to the study. Female participants will first have urine pregnancy testing performed prior to the ultrasound tests; if the participant is found to be pregnant, the participant's participation will end.

A 10 mHz linear array vascular probe for B-mode imaging will be used to visualize the brachial artery. Data will be stored on a compact disc for backup and also on the IU server with password protection. ECG leads will be placed on the participant's chest and automatic blood pressure cuff to left upper arm, set at q.15 minutes. A small forearm cuff is placed on the widest part of the participant's proximal right forearm

(approximately 1-2 cm distal to the antecubital fossa). The brachial artery will then be located with the image optimized for best resolution of all three layers of the anterior and posterior walls (with special emphasis on identifying the media-adventitia interface). Three consecutive cardiac cycles of B-mode images of the brachial artery to the disks will be acquired and stored.

After this baseline evaluation, the measurement of endothelium-dependent vasodilation, or FMD, due to increased blood flow will begin. The forearm pressure cuff will be inflated to 250 mmHg for 5 minutes. At that time, imaging will be switched to B-mode. At 60 and 90 seconds after cuff deflation, three consecutive cardiac cycles of B-mode images of the brachial artery to the disc will be acquired and stored. The greater of the two diameters measured at these time points will be used for FMD analysis.

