6.0 CLINICAL AND LABORATORY EVALUATIONS

6.1 Schedule of Events

Evaluation	Screening Visit	First Entry Visit (within 15 days of Screening)	Second Entry Visit #2 (within 30 days after Screening)	Weekly BtB Sessions for the intervention group (8 in total)	Week 12 Visit (for both groups; 84-105 days after Second Entry Visit)	Week 24/Closeout Visit (for both groups; 168-189 days after Second Entry Visit)
Informed Consent	X					
Documentation of HIV Status	X					
Medical/Psychiatric History	X					
Medication/Supplement Use History	X					
Updated Psychiatric Management			X		X	X
Concomitant/Updated Medications			X		X	X
PHQ-9 Assessment	X	X	X	X	X	X
Signs & Symptoms	X		X		X	X
Diagnoses/Updated Diagnoses	X		X		X	X
Height		X				
Weight		X	X		X	X
Vital Signs	X	X	X		X	X
Brief Physical Examination	X	X	X		X	X
Urine Pregnancy Test	X	X	X		X	X
Randomization			X			
Serum chemistries/glucose, total cholesterol (non-fasting)	X					
Hematology, hemoglobin A1c	X					
HIV-1 RNA level	X		X		X	X
CD4 cell count			X		X	X
Whole blood for ECFCs and monocyte subsets		X	X		X	X
DNA sampling			X			
Beating the Blues Behavioral Intervention				X		
Questionnaires			X		X	X
FMD/NTGMD		X	X		X	X
Frozen Serum for Batched Testing of Inflammatory/Coagulation Markers, Metabolic Markers		X	X		X	X
Frozen Plasma, Serum, and Urine for Future Studies		X	X		X	X

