9.2 Study Design

This trial will be a randomized, controlled, single-blinded, two-arm, parallel group study. Eligible patients will be randomized 1:1 to either *Beating the Blues* (BtB) or Usual Care (UC). Stratifications for

randomization include usage of pharmacologic antidepressants at the Second Entry Visit and sex. Permuted-block randomization will be adopted to ensure the two arms are balanced. Randomization sequences will be prepared by the study statistician and forwarded to the study coordinator.

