9.11 Analysis Plan for Secondary Objectives

Both unadjusted comparisons and adjusted comparisons between UC and BtB will be performed for secondary outcomes defined in 1.2.1-1.2.3. For adjusted comparisons, multiple linear regression models will be constructed to include treatment group, baseline characteristics [demographics, SCL-20 scores, tobacco/exercise/adherence questionnaire results, ART drugs/regimens (including efavirenz (142-144)), antidepressant use, co-morbidities, CD4 cell counts, and HIV-1 RNA levels], and time-varying characteristics (changes in SCL-20 scores, questionnaire results, CD4 cell counts, ART drugs/regimens, HIV-1 RNA levels) to determine their effects on the outcomes. Pearson and Spearman correlation coefficients will be estimated for FMD, IL-6, hsCRP, D-dimer, circulating EPCs/ECFCs levels, and markers of monocyte activation (CD14+CD16+ cell proportions and sCD14/sCD163) with PHQ-9 and SCL-20 scores at baseline. These analyses will be performed for both the intent-to-treat set and the per-protocol set. Dose-response relationships between 12- and 24-week FMD and the number of BtB sessions, which have a range from 0 to 8, will be explored.

Safety assessments will be performed using the safety dataset. HIV-1 RNA levels and CD4 cell counts of the BtB arm during the trial will be summarized and compared to the UC arm.

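### The primary ANCOVA omits the randomization strata and leaves baseline FMD undefined across two Entry Visits: valid as planned, but precision is forgone at almost no cost

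*Combined protocol and SAP*

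**What the plan says.** **Primary model.** Section 9.10 is to "test for treatment group differences in Week 12 FMD adjusted for baseline FMD using the intent-to-treat set", two-sided at 0.05, and repeats this in the per-protocol set. Baseline FMD is the only covariate.

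**Strata.** Section 3.4 (Second Entry Visit) says: "Randomization will be stratified by use of pharmacologic antidepressants at the time of the Second Entry Visit". Section 9.2 says that the stratifications for "randomization include usage of pharmacologic antidepressants at the Second Entry Visit and sex". The two lists differ by sex.

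**Baseline FMD.** Section 3.6: "FMD and NTGMD will be measured according to established guidelines (126) at both Entry Visits", and again at Weeks 12 and 24. Section 3.3 gives the reason: "Two Entry Visits are being conducted in order to establish more precise and stable estimates of endothelial function". No section says how the two values become one baseline. The rule in 3.6 about taking the larger diameter concerns the 60- and 90-second images within one visit.

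**Secondary outcomes.** Objectives 1.2.1 to 1.2.3 compare changes in 18 outcomes, counting EPC/ECFC as one. Section 9.11 plans unadjusted and adjusted comparisons; for the latter, "multiple linear regression models will be constructed to include treatment group, baseline characteristics [demographics, SCL-20 scores, tobacco/exercise/adherence questionnaire results" and further items, among them antidepressant use. SCL-20 is the only one of the 18 whose baseline is listed. The schedule in 6.1 also takes several of these outcomes more than once before randomization, for example "Frozen Serum for Batched Testing of Inflammatory/Coagulation Markers, Metabolic Markers" at both Entry Visits.

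**The concern.** When randomization is stratified on a factor that predicts the outcome, the arms are balanced on it by design. A model without the factor still counts its contribution as residual noise. The estimated standard error is then too large, the interval wider than it need be, and some power is lost.

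The second Entry Visit was added for precision. Its benefit reaches the primary test only if both readings enter the baseline covariate, and the analysis section does not say that they do.

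For the secondary outcomes, comparing raw change scores is less efficient than adjusting for the outcome's own baseline, and the plan does not list that adjustment. All the variables needed are already collected before randomization.

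**Working it through.** **1. The plan's own figure.** From the pilot table (2.3.5), the adjusted difference is 4.18 − 2.47 = 1.71. The pooled SD is √[(12×2.86² + 15×2.72²)/27] = 2.78, so d = 1.71/2.78 = 0.61. The normal approximation gives 2(1.96 + 0.84)²/0.61², which rounds up to 43 per arm. The noncentral t gives 44 (power 79.8% at 43, 80.8% at 44). Then 88/0.80 = 110. Section 9.3 reproduces.

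**2. Cost of adding the strata.** The planned model leaves 88 − 3 = 85 residual degrees of freedom. One or two binary factors leave 84 or 83. At d = 0.61, going from 85 to 83 moves power from 80.75% to 80.73%.

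**3. Gain from adding the strata, by simulation.** From the documents: 110 randomized 1:1 in permuted blocks, 20% attrition, d = 0.61, and 25% women (Section 10.7). Assumed: blocks of 4, data missing at random, both factors used, antidepressant use of 20, 40 or 60%, and a share R² of the residual FMD variance explained by the strata, split equally between them.

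| Setting | R² | Power omitted / included (%) | Type I error omitted (%) |
|---|---|---|---|
| ITT, 20 imputations, use 40% | 0 | 79.0 / 79.2 | 4.6 |
| | 0.05 | 79.4 / 80.9 | 4.7 |
| | 0.10 | 80.4 / 82.8 | 4.5 |
| | 0.20 | 81.3 / 86.8 | 3.4 |
| 88 observed, use 20% | 0 | 79.5 / 79.2 | 4.8 |
| | 0.05 | 80.0 / 81.7 | 4.4 |
| | 0.10 | 80.5 / 83.4 | 4.0 |
| | 0.20 | 82.2 / 88.1 | 3.4 |
| 88 observed, use 60% | 0 | 79.8 / 79.5 | 5.1 |
| | 0.05 | 80.0 / 81.3 | 4.3 |
| | 0.10 | 81.5 / 83.9 | 4.3 |
| | 0.20 | 81.4 / 88.0 | 2.8 |

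The imputation rows use 4,000 replicates, so the Monte Carlo standard error of a 5% rate is √(0.05×0.95/4,000) = 0.34 points. There, 4.5% cannot be told from 5%; 3.4% can. An independent simulation of 88 evaluable participants gave power gains of 0.9, 2.6 and 4.5 points at R² = 0.05, 0.10 and 0.20. With the strata included, type I error was 4.7 to 5.2% in the imputation runs.

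**4. Two baseline readings.** Let r be the correlation of one Entry FMD with Week 12 FMD, and rb the correlation between the Entry Visits. Residual variance is 1 − r² with one reading and 1 − 2r²/(1 + rb) with the mean. The documents give neither r nor rb.

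| r | rb | One reading | Mean | Cut | Power, 44 per arm |
|---|---|---|---|---|---|
| 0.4 | 0.4 | 0.840 | 0.771 | 8.2% | 83.9% |
| 0.4 | 0.8 | 0.840 | 0.822 | 2.1% | 81.6% |
| 0.5 | 0.5 | 0.750 | 0.667 | 11.1% | 85.1% |
| 0.5 | 0.8 | 0.750 | 0.722 | 3.7% | 82.2% |
| 0.6 | 0.6 | 0.640 | 0.550 | 14.1% | 86.2% |
| 0.6 | 0.8 | 0.640 | 0.600 | 6.2% | 83.2% |

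The comparator is 80.8%. This takes the pilot SD as adjusted for one pre-treatment reading, which fits the description in 2.3.5.

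**5. Secondary outcomes, unadjusted comparison.** With equal variances σ² before and after treatment, a change score has variance 2σ²(1 − r), where r is now that outcome's own baseline-to-follow-up correlation. ANCOVA on the outcome's own baseline has σ²(1 − r²). The ratio is (1 + r)/2 = 0.65, 0.75 and 0.85 at r = 0.3, 0.5 and 0.7, a cut of 35, 25 and 15%.

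**The case against.** Section 9.10 already fixes a valid, baseline-adjusted primary test. Baseline FMD absorbs stable differences by sex or antidepressant use, so only what remains counts. If that is 5% or less, the simulated gain is under 2 points. All of this stands, and the size of the gain rests on an R² that the documents do not give.

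The two stratification lists may not conflict in practice. Section 3.4 describes a visit and does not exclude a second factor; 9.2 is the randomization paragraph and contains the first. The repair is one line, but the model cannot name its strata until it is made.

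On baseline FMD, the reason given in 3.3 makes combining the visits the natural reading. The Schema's "withdraws prior to the Baseline/Entry Visit, this participant will be replaced" suggests a single visit, but it concerns replacement of participants and is weak evidence about the analysis. The loss may therefore be nil.

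On the secondary outcomes, 9.11 analyses outcomes that the objectives define as changes, so baseline can enter by subtraction. The 35/25/15% saving is not shown for the adjusted models. They already hold demographics and antidepressant use, so the strata are largely covered there, and they also carry post-randomization changes in SCL-20. The saving assumes normal outcomes, while 9.1 foresees nonparametric methods.

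**Conclusion.** This is a free improvement, not a flaw in validity. A reader might infer that omitting the strata biases the primary estimate or undermines the sample size. Neither follows: the arms are randomized, and 88/110 with about 80% power reproduces.

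Including the strata is worth about 0, 1-2, 2-3 and 5-6 points of power if they explain 0, 5, 10 and 20% of the residual FMD variance, against a loss of at most about 0.3 points if they explain nothing. A reader might also infer that the planned test is materially conservative. Under the planned multiple imputation that is clear only near 20%, where type I error is about 3.4%.

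Using one Entry reading instead of the mean would forgo a 2-14% cut in residual variance, for assumed correlations of 0.4-0.6 with Week 12 and 0.4-0.8 between Entry Visits. If the mean was intended, only the wording is missing. It would go too far to say that the open definition inflates type I error: any one definition fixed in advance holds 5%, and nothing in the documents suggests that the choice would follow the results.

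The secondary saving applies to the unadjusted comparison of normally distributed change scores with equal variances. No secondary power is claimed, because 9.3 does not say which SD its 0.61 refers to.

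**What to change.** - **3.4 and 9.2:** reconcile them so that both state the stratification factors actually used.
- **9.10:** specify an ANCOVA of Week 12 FMD on arm, the mean of the two Entry Visit FMDs (the single value if one is missing) and those stratification factors. Carry the same terms in the imputation model of 9.14.
- **9.11:** for each continuous secondary outcome, make the main comparison an ANCOVA on its own pre-randomization baseline and the stratification factors, transformed or rank-based where 9.1 applies. State how baseline is formed for outcomes measured more than once before randomization.

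The cost is wording, plus 1-2 of 85 residual degrees of freedom in the primary model. No extra participants, visits or measurements are needed.

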9.11 Analysis Plan for Secondary Objectives

Both unadjusted comparisons and adjusted comparisons between UC and BtB will be performed for secondary outcomes defined in 1.2.1-1.2.3. For adjusted comparisons, multiple linear regression models will be constructed to include treatment group, baseline characteristics [demographics, SCL-20 scores, tobacco/exercise/adherence questionnaire results, ART drugs/regimens (including efavirenz (142-144)), antidepressant use, co-morbidities, CD4 cell counts, and HIV-1 RNA levels], and time-varying characteristics (changes in SCL-20 scores, questionnaire results, CD4 cell counts, ART drugs/regimens, HIV-1 RNA levels) to determine their effects on the outcomes. Pearson and Spearman correlation coefficients will be estimated for FMD, IL-6, hsCRP, D-dimer, circulating EPCs/ECFCs levels, and markers of monocyte activation (CD14+CD16+ cell proportions and sCD14/sCD163) with PHQ-9 and SCL-20 scores at baseline. These analyses will be performed for both the intent-to-treat set and the per-protocol set. Dose-response relationships between 12- and 24-week FMD and the number of BtB sessions, which have a range from 0 to 8, will be explored.

Safety assessments will be performed using the safety dataset. HIV-1 RNA levels and CD4 cell counts of the BtB arm during the trial will be summarized and compared to the UC arm.

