1.2 Secondary Objectives

1.2.1 To compare 24-week changes in FMD between those undergoing depression treatment using BtB vs those receiving UC.

1.2.2 To compare 12 and 24-week changes in circulating levels of IL-6, hsCRP, D-dimer, fasting lipid profiles (total cholesterol, HDL-C, LDL-C, triglycerides), insulin resistance estimated using HOMA-IR, systolic and diastolic blood pressures, body mass indices (BMI), circulating EPC/ECFC levels, and circulating markers of monocyte activation (CD14+CD16+ cell proportions and sCD14/sCD163) between those undergoing depression treatment using BtB vs those receiving UC.

1.2.3 To compare 12 and 24-week changes in PHQ-9 scores and SCL-20 scores between those undergoing depression treatment using BtB vs those receiving UC.

1.2.4 To correlate FMD, IL-6, hsCRP, D-dimer, circulating EPCs/ECFCs, and markers of monocyte activation (CD14+CD16+ cell proportions and sCD14/sCD163) levels with PHQ-9 and SCL-20 scores at baseline.

1.2.5 To assess the safety, HIV-1 RNA levels, and CD4 cell counts of the BtB program in HIV-infected adults.

1.2.6 To explore the relationships between genetic markers with FMD, PHQ-9, SCL-20 scores at baseline and with response to depression treatment with BtB.

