2.0 HYPOTHESES, BACKGROUND, AND INTRODUCTION

2.1 Hypotheses

2.1.1 Treatment with BtB will improve FMD, increase circulating EPC/ECFC levels, and reduce circulating levels of IL-6, hsCRP, D-dimer, and markers of monocyte activation (CD14+CD16+ cell proportions and sCD14/sCD163) at both 12 and 24 weeks when compared to UC.

2.1.2 Treatment with BtB will improve PHQ-9 and SCL-20 scores at both 12 and 24 weeks when compared to UC.

2.1.3 Treatment with BtB will be safely tolerated and have no effects on HIV-1 RNA suppression or CD4 cell counts.

2.1.4 Genetic variation is associated with endothelial function, depression severity, and response to depression treatment.

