2.4 Study Rationale

To our knowledge, the current trial is the first ever to test the hypotheses that depressive disorders contribute to greater systemic inflammation, altered coagulation, and endothelial dysfunction in HIV-infected patients and that depression treatment reverses these potential mechanisms of HIV-CVD. Our preliminary data support these hypotheses by finding a strong relationship between depression and a higher risk of incident acute MI in HIV-infected veterans, thereby suggesting a new and, until now, completely unexamined approach (depression treatment) to reducing HIV-CVD events. However, we now need to determine the underlying mechanisms for this association to validate the link between depression and HIV-CVD risk and to justify future large-scale trials. These studies may also open a whole new area of investigation focused on the relationships between mood disorders in general and HIV complications. This application will also test the effects for the first time the *Beating the Blues* therapy program in an HIV-infected population.

We have chosen to use a cognitive behavioral treatment program as our intervention without the addition of pharmacologic antidepressant therapy based on the strength of our preliminary data in which the *Beating the Blues* program alone improved FMD and reduced inflammation. If *Beating the Blues* alone is found to be insufficient to improve depression and CVD risk in the proposed study, then we will investigate in future trials the effects of antidepressants (with and without CBT) on HIV-CVD. We cannot ethically restrict initiation of antidepressant therapies, especially in the Usual Care arm, by the participants' primary providers during the trial, but we will adjust the results for such antidepressant initiation.

We chose to IL-6, hsCRP, and D-dimer as our inflammation and coagulation biomarkers of interest due to their known associations both with depression and HIV-CVD. We will also measure markers of monocyte activation (sCD14, sCD163, $CD14^+CD16^+$ cells) and ECFCs. However, we will also archive plasma, serum, PBMCs, and urine at each visit for future investigation to measure other biomarkers of potential impact on HIV-

CVD if the primary markers are not affected by *Beating the Blues* or if newer and potentially better markers are identified in the literature.

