3.7 Study Questionnaires

We will monitor for changes in depression severity using the PHQ-9 questionnaire. As was done in our pilot trial and the IMPACT trial (48), we will also assess depressive symptoms using the SCL-20, a reliable and valid measure responsive to change (130-133). We will examine total score and % responded ($\geq 50\%$ reduction). We will also assess tobacco use (Tobacco Use Questionnaire from the Behavioral Risk Factor Surveillance System), exercise habits (International Physical Activity Questionnaire), and CVD medication adherence (Morisky Questionnaire). We will also assess anxiety symptoms using the Generalized Anxiety Disorder-7 (GAD-7),(134) hostility/anger using the Buss-Perry Aggression Questionnaire,(135) trait positive affect using the Positive Affect subscale of the Positive and Negative Affect Schedule (PANAS),(136, 137) and sleep quality using the Pittsburgh Sleep Quality Index,(137) all of which are widely used and validated instruments.

Each of these scales is widely used and possesses strong psychometric properties (138-140). Although our focus is on physiologic pathways, we are assessing changes in these factors as they are potential behavioral pathways through which depression and its treatment may influence the outcomes (141).

These questionnaires will be administered in private with availability of the study team to assist only when asked by the participant. The participant may refuse to complete any of the questionnaires.

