10.0 HUMAN PARTICIPANTS RESEARCH AND PROTECTION

10.1 General Considerations/Investigator Training

The Human Participants Research outlined in this proposal meets the definition of a Phase II clinical trial for the purpose of identifying biological and physiological mechanisms of human disease (not for identifying the superiority of one agent over the other). Therefore, a formal Data and Safety Monitoring Board is not required, although appropriate monitoring through the Data and Safety Monitoring Plan with independent monitor as described below will be fully implemented. This trial will be posted on ClinicalTrials.gov and updated regularly as needed for protocol updates and results. All Indiana University personnel involved with this application have successfully completed the training and examination involved with the Collaborative Institutional Training Initiative Course.

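### The adjusted secondary comparisons in 9.11 condition on changes measured after randomization, so their arm coefficient is not the effect of assignment to BtB, and no secondary comparison is named as the leading one

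*Combined protocol and SAP*

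**What the plan says.** Section 9.11 opens with "Both unadjusted comparisons and adjusted comparisons between UC and BtB will be performed for secondary outcomes defined in 1.2.1-1.2.3". Its adjusted comparisons are multiple linear regressions containing treatment group, a list of baseline characteristics and "time-varying characteristics (changes in SCL-20 scores, questionnaire results, CD4 cell counts, ART drugs/regimens, HIV-1 RNA levels) to determine their effects on the outcomes". They are run on both the intent-to-treat and per-protocol sets. One covariate list serves every outcome in 1.2.1-1.2.3. That range includes 1.2.3: "To compare 12 and 24-week changes in PHQ-9 scores and SCL-20 scores".

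Elsewhere the protocol says how these variables relate to treatment:

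- Hypothesis 2.1.2 expects BtB to improve PHQ-9 and SCL-20.
- Section 3.7 (Study Questionnaires) tracks the questionnaire factors because "they are potential behavioral pathways through which depression and its treatment may influence the outcomes".
- Hypothesis 2.1.3 expects BtB to "have no effects on HIV-1 RNA suppression or CD4 cell counts".
- Section 10.1 classes the trial as one "for the purpose of identifying biological and physiological mechanisms of human disease".

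The primary analysis in 9.10 is an ANCOVA for "treatment group differences in Week 12 FMD adjusted for baseline FMD using the intent-to-treat set", with no post-randomization term. On antidepressants started during the trial, section 2.4 says "we will adjust the results for such antidepressant initiation". Section 9.10 has no such term, and 9.11 lists antidepressant use only among the baseline characteristics.

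**The concern.** Randomization protects a comparison of the arms as assigned, and adjustment for covariates fixed before randomization keeps that protection. Adjustment for something treatment may have changed does not. The arm coefficient then describes the difference between arms among participants with the same SCL-20 and questionnaire changes, which is not what objectives 1.2.1-1.2.3 ask.

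Two things can follow. If part of the BtB effect runs through the adjusted changes, the coefficient shrinks toward zero. If a change and the outcome share an unmeasured cause, it can be biased in either direction, even when BtB has no effect. CD4, ART and HIV-1 RNA changes are also post-randomization, but nothing in the documents shows them to be mediators.

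The two planned comparisons therefore estimate different quantities and may disagree, and the plan gives no rule for which one is the BtB result. Section 9.1 lets the analysis plan change without an amendment unless a significant feature changes, so the choice could be made after results are seen.

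Antidepressant initiation raises the same problem. Section 3.4 (Second Entry Visit) has primary providers told the assignment, so initiation can depend on arm, and adjusting for it would condition on another possible consequence of assignment.

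**Working it through.** **The plan's own figure.** The pilot table in 2.3.5 gives adjusted post-treatment FMD of 4.18 (SD 2.86) and 2.47 (SD 2.72). With 13 and 16 patients, the pooled SD is √[(12×2.86² + 15×2.72²)/27] = 2.78, so d = 1.71/2.78 = 0.61. A two-sided t-test at 0.05 with 44 per arm and d = 0.61 has power 0.808, and 88/0.80 = 110. The sample size in 9.3 reproduces and is not in dispute.

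**Inputs.** From the documents: 44 per arm (9.3), effect 0.61 SD (9.3) and SCL-20 effect d = 1.33 (2.3.5, HIV-uninfected patients). Assumed, because the documents do not give them: the mediated share m and the within-arm correlation r produced by a shared cause.

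**Model.** Within-arm SDs are 1. T is arm and M is SCL-20 reduction, so M = d·T + e. The outcome is Y = (1−m)·0.61·T + b·M + noise, with b = m·0.61/d. The total effect is 0.61 whatever m is. Regressing Y on T and M gives an expected arm coefficient of (1−m)·0.61. The variance inflation for T is 1 + d²/4 = 1 + 1.33²/4 = 1.44, so its standard error is multiplied by √1.44 = 1.20. Power comes from 10,000 simulated trials per row.

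| m | Implied slope b | Arm coefficient (SD) | Power, adjusted | Power, unadjusted |
|---|---|---|---|---|
| 0 | 0.00 | 0.61 | 0.65 | 0.81 |
| 0.25 | 0.11 | 0.46 | 0.43 | 0.81 |
| 0.50 | 0.23 | 0.31 | 0.22 | 0.81 |
| 0.75 | 0.34 | 0.15 | 0.10 | 0.81 |
| 1 | 0.46 | 0.00 | 0.05 | 0.81 |

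With a smaller assumed SCL-20 effect and m = 0.50, power is 0.29 at d = 0.8 and 0.41 at d = 0.5. The last case needs a slope of 0.61.

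**No BtB effect, shared unmeasured cause.** Suppose larger SCL-20 reductions go with higher outcome values for reasons unrelated to arm. The adjusted arm coefficient then averages −r·d, although the true effect is zero. At r = 0.2 and d = 1.33 this is −0.27 SD, or −0.27×2.78 ≈ −0.7 FMD percentage points. At r = 0.4 it is −0.53 SD, or about −1.5 points. With r of the opposite sign, the bias is upward. Two-sided type I error:

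| r | d = 1.33 | d = 0.8 | d = 0.5 |
|---|---|---|---|
| 0.19 | 0.17 | 0.10 | 0.07 |
| 0.4 | about 0.6 | 0.32 | 0.17 |

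The value 0.19 is the size of the cross-sectional depression-FMD correlation cited in 2.2.3.

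**SCL-20 as the outcome.** Follow-up equals baseline plus change. Regressing follow-up on arm, baseline and same-visit change therefore gives coefficients 0, 1 and 1. With change as the outcome, it appears on both sides and the arm coefficient is again 0. A numerical check gave zero to machine precision.

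**PHQ-9 as the outcome.** The documents give no PHQ-9 effect. If it equals the SCL-20 effect d, and the within-arm correlation of the two changes is r, the adjusted effect is d·(1−r). At assumed r of 0.5 to 0.8, 50% to 20% of the true effect remains.

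**The case against.** The strongest reply is that these models are explanatory. Section 9.11 says they serve to determine covariate effects, 3.7 gives pathways as the reason for measuring those factors, and 10.1 puts mechanism ahead of superiority. The unadjusted comparisons are planned for every outcome, so no estimate of the effect of assignment is lost. This is a fair reading and limits the reach of the point. It does not remove it: 9.11 introduces the models as adjusted comparisons between the arms and never calls them exploratory or mediation analyses. The plan does use such labels elsewhere, for subgroups (9.13) and dose-response (9.11).

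The sizes can also be challenged. The SCL-20 effect comes from 13 versus 16 patients, and the reported p = 0.02 does not fit d = 1.33 at those numbers: t = 1.33×√(13×16/29) = 3.56, p about 0.001. The analysed numbers may have been smaller. A smaller d or r lowers the type I error considerably, and high mediated shares need fairly steep within-arm slopes. The planned baseline covariates could recover some precision. All of this stands, so the figures are a range under stated assumptions and not a forecast.

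The exact zero for SCL-20 needs the same-visit change to be used and the list to be applied unedited. A Week 12 change in a Week 24 model would not force it. Section 9.11 excludes neither use.

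Naming the unadjusted comparison as the lead would settle the ranking equally well. It would still leave the adjusted models mislabelled.

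**Conclusion.** The concern holds. As written, the adjusted comparisons in 9.11 do not estimate the effect of assignment to BtB, and nothing says whether the adjusted or unadjusted result leads. This follows from the text and needs no assumption; only the size does. At the pilot SCL-20 effect, power falls from 0.81 to between 0.65 (nothing mediated) and 0.05 (all mediated). With no true effect, type I error ranges from 0.07 (r = 0.19, d = 0.5) to about 0.6 (r = 0.4, d = 1.33). For SCL-20 itself, a model with same-visit change carries no information about the arms.

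The primary ANCOVA and the unadjusted secondary comparisons are sound. The antidepressant statement in 2.4 has no counterpart in 9.10 or 9.11. This should be fixed before analysis, but it does not threaten the primary result.

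**What to change.** 1. In 9.11, limit the adjusted arm comparison to covariates fixed before randomization, including the baseline value of the outcome and the stratification factors. Name it as the main secondary analysis, which matches the form of 9.10. Sections 3.4 and 9.2 disagree on whether sex is a stratification factor, so settle that first.
2. Move every post-randomization change to a separate analysis labelled exploratory mediation, with its assumption of no unmeasured common causes stated. Do not use SCL-20 change as a covariate when SCL-20 is the outcome.
3. Reconcile 2.4 with 9.10 and 9.11. Report antidepressant initiation by arm, and keep the comparison by assigned arm as the effect estimate.

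The cost is wording in 9.11 and one sentence in 2.4. No new data and no change in sample size are needed, and the mechanism question keeps its own analysis.
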